11.3 Audit and inspection

Inspections by regulatory health authority representatives i.e. FDA and IEC(s)/IRB(s) are possible. The investigator should notify Bayer and Merck immediately of any such inspection.

The investigator/institution agrees to allow the auditor or inspector direct access to all relevant documents and allocate his/her time and the time of his/her staff to the auditor/inspector to discuss findings and any issues. Audits and inspections may occur at any time during or after completion of the study

See section 11.2 for further details.

11.4 Archiving

Essential documents shall be archived safely and securely in such a way that ensures that they are readily available upon authorities' request.

Patient (hospital) files will be archived according to local regulations and in accordance with the maximum period of time permitted by the hospital, institution or private practice. The investigator/institution notifies the sponsor if the archival arrangements change (e.g. relocation or transfer of ownership). The investigator/institution site file is not to be destroyed without the approval of Bayer and Merck)

12. Premature termination of the study

- If risk-benefit ratio becomes unacceptable owing to, for example,
 - Safety findings from this study (e.g. SAEs)
 - Results of any interim analysis
 - Results of parallel clinical studies
 - Results of parallel animal studies
(on e.g. toxicity, teratogenicity, carcinogenicity or reproduction toxicity).
- If the study conduct (e.g. recruitment rate; drop-out rate; data quality; protocol compliance) does not suggest a proper completion of the trial within a reasonable time frame.

The investigator has the right to close his/her center at any time.

For any of the above closures, the following applies:

- Closures should occur only after consultation between involved parties.
- All affected institutions (e.g. IEC(s)/IRB(s); competent authority(ies); study center; head of study center) must be informed as applicable according to local law.
- In case of a partial study closure, ongoing subjects, including those in post study follow-up, must be taken care of in an ethical manner.

Details for individual subject's withdrawal can be found in Section 5.2.1.

13. Ethical and legal aspects

13.1 Ethical and legal conduct of the study

The procedures set out in this protocol, pertaining to the conduct, evaluation, and documentation of this study, are designed to ensure that the investigator abide by Good Clinical Practice (GCP) guidelines and under the guiding principles detailed in the Declaration of Helsinki. The study will also be carried out in keeping with applicable local law(s) and regulation(s).

Documented approval from appropriate IEC(s)/IRBs will be obtained for all participating centers before start of the study, according to GCP, local laws, regulations and organizations. When necessary, an extension, amendment or renewal of the EC/IRB approval must be obtained and also forwarded to Bayer.

Strict adherence to all specifications laid down in this protocol is required for all aspects of study conduct; the investigator may not modify or alter the procedures described in this protocol.

Modifications to the study protocol will not be implemented by the investigator without discussion and agreement by Bayer. However, the investigator may implement a deviation from, or a change of, the protocol to eliminate an immediate hazard(s) to the trial subjects without prior IEC/IRB/Bayer approval/favorable opinion. As soon as possible, the implemented deviation or change, the reasons for it and if appropriate the proposed protocol amendment should be submitted to the IEC/IRB/head of medical institution. Any deviations from the protocol must be explained and documented by the investigator.

The Principal Investigator is responsible for the conduct of the clinical trial at the site in accordance with Title 21 of the Code of Federal Regulations and/or the Declaration of Helsinki. The Principal Investigator is responsible for personally overseeing the treatment of all study patients. The Principal Investigator must assure that all study site personnel, including sub-investigators and other study staff members, adhere to the study protocol and all FDA/GCP/NCI regulations and guidelines regarding clinical trials both during and after study completion.

The Principal Investigator at each institution or site will be responsible for assuring that all the required data will be collected and properly documented.

13.2 Subject information and consent

Each subject / legal representative or proxy consentor will have ample time and opportunity to ask questions and will be informed about the right to withdraw from the study at any time without any disadvantage and without having to provide reasons for this decision.

Only if the subject / legal representative or proxy consentor voluntarily agrees to sign the informed consent form and has done so, may he/she enter the study. Additionally, the investigator and other information provider (if any) will personally sign and date the form. The subject / legal representative or proxy consentor will receive a copy of the signed and dated form.

The signed informed consent statement is to remain in the investigator site file or, if locally required, in the patient's note/file of the medical institution.

In the event that informed consent is obtained on the date that baseline study procedures are performed, the study record or subject's clinical record must clearly show that informed consent was obtained prior to these procedures.

1. If the patient is not capable of providing a signature, a verbal statement of consent can also be given in the presence of an impartial witness (independent of Bayer and the investigator). This is to be documented by a signature from the informing physician as well as by a signature from the witness.
2. For minors or adults under legal protection, consent shall be given by the legal guardian(s). The consent of a minor or adult under legal protection shall also be requested where such a person is able to express his/her own will. His/her refusal or the withdrawal of his/her consent may not be disregarded.
3. In emergency situations, when prior consent of the patient is not possible, the consent of the patient's legal representative(s) or proxy consentor, if present, should be requested. The patient should be informed about the study as soon as possible and his/her consent to continue the study should be requested.

The informed consent form and any other written information provided to subjects / legal representatives or proxy consentors will be revised whenever important new information becomes available that may be relevant to the subject's consent, or there is an amendment to the protocol that necessitates a change to the content of the subject information and / or the written informed consent form. The investigator will inform the subject / legal representative or proxy consentor of changes in a timely manner and will ask the subject to confirm his/her participation in the study by signing the revised informed consent form. Any revised written informed consent form and written information must receive the IEC/IRB's approval / favorable opinion in advance of use.

13.3 Publication policy

Bayer recognizes the right of the investigator to publish results upon completion of the study. However, the investigator must send a draft manuscript of the publication or abstract to Bayer at least thirty days in advance of submission in order to obtain approval prior to submission of the final version for publication or congress presentation. This will be reviewed promptly and approval will not be withheld unreasonably. In case of a difference of opinion between Bayer and the investigator(s), the contents of the publication will be discussed in order to find

a solution which satisfies both parties. All relevant aspects regarding data reporting and publication will be part of the contract between Bayer and the investigator/institution

The Principal Investigator should ensure that the information regarding the study be publicly available on the internet at www.clinicaltrials.gov.

15.1 Examples of a low fat meal

Two slices of white toast with 1 tablespoon of low-fat margarine and 1 tablespoon of jelly and 8 ounces of skim milk. (Approximately 319 calories and 8.2 grams of fat)

One cup of cereal (i.e. Special K), 8 ounces of skimmed milk, one piece of toast with jam (no butter or marmalade), apple juice, and one cup of coffee or tea (2 g fat, 17 g protein, 93 g of carbohydrate, 520 calories).

15.2 Toxicity management guidelines for immune-related AEs associated with pembrolizumab

General instructions:				

 1. Corticosteroid taper should be initiated upon AE improving to Grade 1 or less and continue to taper over at least 4 weeks. 2. For situations where pembrolizumab has been withheld, pembrolizumab can be resumed after AE has been reduced to Grade 1 or 0 and corticosteroid has been tapered. Pembrolizumab should be permanently discontinued if AE does not resolve within 12 weeks of last dose or corticosteroids cannot be reduced to ≤ 10 mg prednisone or equivalent per day within 12 weeks. 3. For severe and life-threatening irAEs, IV corticosteroid should be initiated first followed by oral steroid. Other immunosuppressive treatment should be initiated if irAEs cannot be controlled by corticosteroids. 				
Pneumonitis	Grade 2	Withhold	
 Administer corticosteroids (initial dose of 1-2 mg/kg prednisone or equivalent) followed by taper 	
 Monitor participants for signs and symptoms of pneumonitis Evaluate participants with suspected pneumonitis with radiographic imaging and initiate corticosteroid treatment Add prophylactic antibiotics for opportunistic infections
	Grade 3 or 4, or recurrent Grade 2	Permanently discontinue		
Diarrhea / Colitis	Grade 2 or 3	Withhold	
 Administer corticosteroids (initial dose of 1-2 mg/kg prednisone or equivalent) followed by taper 	
 Monitor participants for signs and symptoms of enterocolitis (ie, diarrhea, abdominal pain, blood or mucus in stool with or without fever) and of bowel perforation (ie, peritoneal signs and ileus). Participants with \geq Grade 2 diarrhea suspecting colitis should consider GI consultation and performing endoscopy to rule out colitis. Participants with diarrhea/colitis should be advised to drink liberal quantities of clear fluids. If sufficient oral fluid intake is not feasible, fluid and electrolytes should be substituted via IV infusion.
	Grade 4	Permanently discontinue		
AST / ALT elevation or Increased bilirubin	Grade 2	Withhold	
 Administer corticosteroids (initial dose of 0.5- 1 mg/kg prednisone or equivalent) followed by taper 	
 Monitor with liver function tests (consider weekly or more frequently until liver enzyme value returned to baseline or is stable)
	Grade 3 or 4	Permanently discontinue	
 Administer corticosteroids (initial dose of 1-2 mg/kg prednisone or equivalent) followed by taper 	
Type 1 diabetes mellitus (T1DM) or Hyperglycemia	Newly onset T1DM or Grade 3 or 4 hyperglycemia associated with evidence of β -cell failure	Withhold	
 Initiate insulin replacement therapy for participants with T1DM Administer anti-hyperglycemic in participants with hyperglycemia 	
 Monitor participants for hyperglycemia or other signs and symptoms of diabetes.
Hypophysitis	Grade 2	Withhold	
 Administer corticosteroids and initiate hormonal replacements as clinically indicated. 	
 Monitor for signs and symptoms of hypophysitis (including hypopituitarism and adrenal insufficiency)
	Grade 3 or 4	Withhold or permanently discontinue ¹		
Hyperthyroidism	Grade 2	Continue	
 Treat with non-selective beta-blockers (eg, propranolol) or thionamides as appropriate 	
 Monitor for signs and symptoms of thyroid disorders.

	Grade 3 or 4	Withhold or permanently discontinue ¹		
Hypothyroidism	Grade 2-4	Continue	
Initiate thyroid replacement hormones (eg, levothyroxine or liothyronine) per standard of care	
Monitor for signs and symptoms of thyroid disorders.
Nephritis and Renal dysfunction	Grade 2	Withhold	
Administer corticosteroids (prednisone 1-2 mg/kg or equivalent) followed by taper.	
Monitor changes of renal function
	Grade 3 or 4	Permanently discontinue		
Myocarditis	Grade 1 or 2	Withhold	
Based on severity of AE administer corticosteroids	
Ensure adequate evaluation to confirm etiology and/or exclude other causes
	Grade 3 or 4	Permanently discontinue		
All other immune-related AEs	Intolerable/persistent Grade 2	Withhold	
Based on type and severity of AE administer corticosteroids	
Ensure adequate evaluation to confirm etiology and/or exclude other causes
	Grade 3	Withhold or discontinue based on the type of event. Events that require discontinuation include and not limited to: Guillain-Barre Syndrome, encephalitis		
	Grade 4 or recurrent Grade 3	Permanently discontinue		

1. Withhold or permanently discontinue pembrolizumab is at the discretion of the investigator or treating physician.

NOTE:

For participants with Grade 3 or 4 immune-related endocrinopathy where withhold of pembrolizumab is required, pembrolizumab may be resumed when AE resolves to ≤ Grade 2 and is controlled with hormonal replacement therapy or achieved metabolic control (in case of T1DM). ⁱ

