We propose to combine regorafenib and PD1 (pembrolizumab) in colorectal cancer patients in 3rd and 4th line setting. Using a phase I/II design, we will first enroll 3-18 patient on phase I to find the recommended dose for phase II. We will then accrue patients to the phase II portion of the trial with the primary efficacy endpoint of PFS. An extensive biomarker analysis, liquid biopsies and tumor tissue, is planned to identify the population who would most benefit from this combination.

Four patients on dose level 1: 80mg were reviewed by the Phase I DLT Committee. One patient was deemed inevaluable for DLT and was replaced. Three patients were evaluable with no DLT. The trial was recommended to proceed to accrue three patients to dose level 2: 120mg. All three patients at this dose level had either grade 2 or grade 3 rash which required a dose reduction at either cycle 2 or 3. It was determined that the dose level 2: 120mg would

be challenging due to its overall tolerability; therefore, dose level 1: 80mg was recommended to expand and enroll additional three patients for a total of 6 patients to be reviewed.

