Grade 2	1 st occurrence	Consider decreasing dose by one dose level and immediately institute supportive measures. If no improvement, interrupt therapy for a minimum of 7 days, until toxicity resolves to Grade 0-1 ^{b, c}
	No improvement within 7 days or 2 nd occurrence	Interrupt therapy until toxicity resolves to Grade 0-1. ^c When resuming treatment, treat at reduced dose level ^b If dose reduced from the 1 st occurrence then discontinue therapy.
	3 rd occurrence	Discontinue therapy
	4 th occurrence	Discontinue therapy
Grade 3	1 st occurrence	Institute supportive measures immediately. Interrupt therapy for a minimum of 7 days until toxicity resolves to Grade 0-1. ^c When resuming treatment, decrease dose by one dose level. ^{b, d}
	2 nd occurrence	Discontinue therapy
	3 rd occurrence	Discontinue treatment permanently.

a. More conservative management is allowed if judged medically appropriate by the investigator.
 
b. If toxicity returns to Grade 0-1 after dose reduction, dose re-escalation is permitted at the discretion of the investigator if subject has completed one cycle at reduced dose without recurrence of event.
 
c. If there is no recovery after a 4-week delay, treatment with regorafenib will be discontinued permanently.
 
d. Subjects requiring > 1 dose reductions should go off protocol therapy.
 
e. The maximum daily dose is 80 mg. If reduction required resulting in a dose of less than 80mg qod of regorafenib, then regorafenib will be permanently discontinued.
		

Specific guidance for skin and subcutaneous disorders other than HFSR (includes rash, rash erythematous, rash follicular, rash generalized, rash macular, rash maculopapular, rash papular, rash pruritic, exfoliative rash, pruritus, eczema, dermatitis)		
Event	Regorafenib	Pembrolizumab
G2	
 No modifications 	
 Consider withholding for persistent symptoms Restart at same dose if resolution to ≤ G1 or baseline ≤ 12 weeks of last infusion Consider discontinuation if NO resolution ≤ 12 weeks of last infusion ¹

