G3	
 • Hold until recovery to \leq G2 and restart at same dose level or reduce 1 dose level ^a (at the investigator's discretion) • 1st + 2nd re-appearance: Hold until recovery to \leq G2 and reduce 1 dose level ^a (at the investigator's discretion) • 3rd re-appearance: Discontinue 	
 • Hold and restart at same dose if resolution to \leq G1 or baseline \leq 12 weeks of last infusion • Hold and discontinue if NO resolution \leq 12 weeks of last infusion ^b
G4 (when applicable)	
 • Hold until recovery to \leq G2 and reduce 1 dose level ^a • 1st re-appearance: Discontinue 	
 • Discontinue ^b

¹ If toxicity returns to Grade 0-1 after dose reduction, dose re-escalation is permitted at the discretion of the investigator if subject has completed one cycle at reduced dose without recurrence of event.

a: If reductions are required resulting in a dose of less than 80 mg q.o.d. of regorafenib, then regorafenib will be permanently discontinued. For grade 3, patient could stay on regorafenib for the first appearance, or hold until resolved to grade 2 or less, restart at the same dose level or lower after discussion between investigator and study chair.

b: after consultation with study chair, if toxicity considered at least possibly related to pembrolizumab.

If reduction required resulting in a dose of less than 80mg qod of regorafenib, then regorafenib will be permanently discontinued.

(For studies with combination therapy, consider including the following statement "The other study treatment may be continued").

At first occurrence of HFSR, independent of grade, prompt institution of supportive measures such as topical emollients, low potency steroids, or urea-containing creams should be administered.

Recommended prevention/management strategies for skin toxicities consistent with HFSR are summarized below:

Control of calluses

Before initiating treatment with regorafenib:

- Check condition of hands and feet.
- Suggest a manicure/pedicure, when indicated.
- Recommend pumice stone use for callus or 'rough spot' removal.

During regorafenib treatment:

- Avoid pressure points.
- Avoid items that rub, pinch or create friction.

Use of creams

- Non-urea based creams may be applied liberally.

- Keratolytic creams (e.g. urea-based creams, salicylic acid 6%) may be used sparingly and only to affected (hyperkeratotic) areas.

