7.3.1.1.3 Immune-mediated adverse reactions

Immune-mediated adverse reactions occurred in patients receiving pembrolizumab. In clinical trials, most immune-mediated adverse reactions were reversible and managed with interruptions of pembrolizumab, administration of corticosteroids and/or supportive care.

For suspected immune-mediated adverse reactions, ensure adequate evaluation to confirm etiology or exclude other causes. Based on the severity of the adverse reaction, withhold pembrolizumab and administer corticosteroids (see below). Upon improvement to Grade 1 or less, initiate corticosteroid taper and continue to taper over at least 1 month. Restart pembrolizumab if the adverse reaction remains at Grade 1 or less. If another episode of a severe adverse reaction occurs, permanently discontinue pembrolizumab.

Immune-mediated pneumonitis

Pneumonitis has been reported in patients receiving pembrolizumab. Monitor patients for signs and symptoms of pneumonitis. If pneumonitis is suspected, evaluate with radiographic imaging. Exclude other causes of pneumonitis, and manage treatment in accordance with the guidelines above. Administer corticosteroids, withhold pembrolizumab for moderate (Grade 2) pneumonitis, and permanently discontinue pembrolizumab for severe (Grade 3) or life-threatening (Grade 4) pneumonitis (see Immune-mediated adverse reactions above). If Grade 2 pneumonitis is repeated pembrolizumab will be discontinued permanently.

Immune-mediated colitis

Colitis has been reported in patients receiving PEMBROLIZUMAB. Monitor patients for signs and symptoms of colitis. Exclude other causes of colitis, and manage treatment in accordance with the guidelines above. Administer corticosteroids, withhold pembrolizumab for moderate (Grade 2) or severe (Grade 3) colitis, and permanently discontinue pembrolizumab for life-threatening (Grade 4) colitis (see Immune-mediated adverse reactions above).

Immune-mediated hepatitis

Hepatitis has been reported in patients receiving pembrolizumab. Monitor patients for changes in liver function (at the start of treatment, periodically during treatment and as indicated based on clinical evaluation) and symptoms of hepatitis. Exclude other causes of hepatitis, and manage treatment in accordance with the guidelines above. Administer corticosteroids and, based on severity of liver enzyme elevations, withhold or discontinue pembrolizumab (see Immune-mediated adverse reactions above).

Immune-mediated nephritis

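### For an immune-related rash that recurs at Grade 3 and resolves in time, the skin table has no pembrolizumab recurrence stop, while Appendix 15.2 and Section 7.3.1.1.3 stop it permanently

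*Combined protocol and SAP*

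**What the plan says.** Four places bear on pembrolizumab after a Grade 3 rash.

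- **Section 6.3.1, skin table.** It is headed "Specific guidance for skin and subcutaneous disorders other than HFSR (includes rash" and further skin conditions), and the heading sets no limit by cause. At Grade 3 the pembrolizumab column reads "Hold and restart at same dose if resolution to" Grade 1 or baseline within 12 weeks of the last infusion. The other branch is "Hold and discontinue if NO resolution" within that time. Footnote b ties discontinuation to consultation with the study chair and to an event at least possibly related to pembrolizumab.
- **Appendix 15.2.** Its title is "Toxicity management guidelines for immune-related AEs associated with pembrolizumab". It has no row for rash. The last row, "All other immune-related AEs", gives permanent discontinuation for "Grade 4 or recurrent Grade 3".
- **Section 7.3.1.1.3, opening text on immune-mediated reactions.** "If another episode of a severe adverse reaction occurs, permanently discontinue pembrolizumab".
- **Section 7.3.1.1.3, general irAE table.** Grades 3 and 4 share one row: withhold, and discontinue if steroids cannot be brought down within 12 weeks. It has no rule for a recurrent Grade 3 event.

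The hepatic guidance in Section 6.3.1 ends by sending the reader to appendix 2, section 16.2, for pembrolizumab toxicity management. The document has no section 16; the appendix is numbered 15.2.

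**The concern.** Rash is a relevant toxicity in this trial. Section 1.1 reports of the 120 mg level: "All three patients at this dose level had either grade 2 or grade 3 rash which required a dose reduction". A site treating a rash would naturally open the table written for rash, and the pembrolizumab column there gives no sign that a second Grade 3 event is treated differently elsewhere. A site that opens the appendix finds a permanent stop.

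Two things are at stake. The first is re-exposure to pembrolizumab after a second severe immune-related skin event. The second is consistency of the tolerability measure. Section 7.2 defines tolerability as the median duration of combination therapy, and Section 4 judges it on a step from 1.7 to 2.0 months. If sites follow different tables, some patients' combination therapy ends under one rule and some under another.

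**Working it through.** No sample size, error rate or event count is involved, so there is nothing to recompute. The check sets the rules side by side.

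**Can an immune-related rash fall under both texts?** Yes. The skin table is not limited by cause, and its footnote b expressly considers events possibly related to pembrolizumab. Appendix 15.2 has no rash row, so an immune-related rash lands in its catch-all row. Section 7.3.1.1.3 lists severe skin reactions among the immune-mediated reactions reported with pembrolizumab.

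**What does each text do, case by case?**

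| Rash (not HFSR) | Skin table, pembrolizumab | Appendix 15.2 | Opposed? |
|---|---|---|---|
| Grade 2, immune-related | Consider withholding if persistent | Withhold if intolerable or persistent | No |
| First Grade 3, immune-related, resolves within 12 weeks | Hold, then restart | Withhold or discontinue, depending on the event | No |
| Recurrent Grade 3, immune-related, resolves within 12 weeks | Restart condition met; recurrence not mentioned | Permanent stop (Section 7.3.1.1.3 agrees) | **Yes, read literally** |
| Recurrent Grade 3, immune-related, not resolved within 12 weeks | Discontinue (footnote b) | Permanent stop | No |
| Recurrent Grade 3, not judged immune-related | Hold, then restart or discontinue | Does not apply | No |
| Grade 4, immune-related | Discontinue (footnote b) | Permanent stop | No |

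One case out of six is opposed.

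**Is the missing recurrence rule just a matter of table style?** Two comparisons suggest not. In the same Grade 3 row, the regorafenib cell counts a first, second and third re-appearance, so the row anticipates repeat events. In the diarrhea table (Table 6.7), the pembrolizumab column does make recurrent Grade 3 a trigger for permanent discontinuation. The skin table's pembrolizumab cell has nothing equivalent.

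**Does anything set precedence?** No section says which table governs a rash. The pointer after the hepatic guidance leads to a section number that does not exist. The general irAE table does not settle the matter either, because it has no recurrence rule for Grade 3.

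**The case against.** The strongest reply is that the skin table is silent on recurrence and does not authorise a second restart. On that view the texts can be read together: the skin table handles a Grade 3 event, and Appendix 15.2 and Section 7.3.1.1.3 add the recurrence rule once the event is judged immune-related. The pointer to the pembrolizumab guidance, though misnumbered, can only mean Appendix 15.2 and is worded generally. Footnote b also brings the study chair into a discontinuation decision.

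Part of this stands. The skin table does not expressly order re-infusion after a second event, and a careful reader could reach the appendix. It does not remove the conflict. The restart instruction is not limited to a first event, so its condition is met again each time the rash settles. The pointer sits in the liver guidance, and footnote b attaches to the discontinuation entries, not to the restart.

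Three stronger readings are tempting, and the documents do not support them.

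- A reader might infer that every recurrent Grade 3 rash meets opposite instructions. Appendix 15.2 and the rule in Section 7.3.1.1.3 apply only to immune-related events, and the latter first asks the site to confirm the cause or exclude others.
- A reader might infer that the 120 mg patients would have received opposite pembrolizumab decisions. Section 1.1 reports Grade 2 or Grade 3 rash with dose reduction. It gives no separate Grade 3 count, no recurrence and no immune attribution. It also says that 80 mg was the level recommended for expansion.
- A reader might infer that the skin table allows two further pembrolizumab restarts, after the first and second re-appearance. That count belongs to the regorafenib column and cannot be carried across.

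**Conclusion.** The inconsistency is real and narrow. It arises for a rash other than HFSR that is judged immune-related, recurs at Grade 3, and resolves to Grade 1 or baseline within 12 weeks of the last infusion. There the skin table, taken literally, leads to a restart at the same dose, while Appendix 15.2 and Section 7.3.1.1.3 lead to permanent discontinuation.

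The conclusion rests on two readings: that an immune-related rash belongs in the appendix's catch-all row, since no other row fits, and that a restart instruction not limited to first events applies to later ones. If the cell is instead read as silent, the defect becomes an omission in the table that sites will use for rash. The remedy is the same.

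Its size cannot be given. The documents report no rate of recurrent immune-related Grade 3 rash on the combination, so neither the number of patients affected nor any shift in median treatment duration can be derived. The 120 mg experience shows that rash matters in this trial and nothing more. The point warrants correction because it concerns re-exposure after a severe event and costs little to put right. This review takes no position on which clinical rule is correct.

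**What to change.** Reconcile the skin table, both parts of Section 7.3.1.1.3 and Appendix 15.2:

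1. In the skin table's Grade 3 pembrolizumab cell, state the action when Grade 3 recurs.
2. State which table governs a rash considered at least possibly related to pembrolizumab.
3. Bring the Grade 3 entry of the general irAE table into line with whatever is decided.
4. Correct the pointer after the hepatic guidance so that it cites Section 15.2.

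The clinical lead decides the action at recurrence. The cost is amendment wording in a few table cells and one corrected cross-reference. Sample size, endpoints and analysis are unchanged.
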